2.4.3 Exploratory outcomes

Intraoral photographs

An intraoral photograph was taken at the time of the completion of the WHO mucositis score at the 4 month visit. This was anonymised for independent fully blinded evaluation (using the WHO mucositis score) by another member of the research team.

2.5 Study assessments

See protocol version 4.0 Section 13.6 for a detailed list of all study assessments and section 13.7 for a schedule of events.

2.6 Sample size and power

Original Sample Size

The original sample size calculation for this trial required a total of 380 patients. This comprised of a minimum of 100 patients recruited during the pilot phase of the trial with the remaining patients being recruited during the main trial phase.

This primary outcome measure is the OMWQ-HN score at 6 weeks following start of irradiation. According to Epstein 2007, a group difference of 4 points reflects a meaningful treatment effect and at 6 weeks and the standard deviation of the OMWQ-HN is 10.7. The trial was powered with small and acceptable errors of 5% α and 10% β . A total of 152 patients with primary outcome data are required in each treatment group to be able to detect this size of clinically relevant difference with 90% power. The sample size was inflated to 190 patients recruited in each trial arm assuming a maximum of 20% drop-out or missing data.

Closure of the trial prior to reaching the original target sample size

Due to the lack of patient recruitment the HTA requested that plans be drawn up to manage the closure of the trial prior to reaching the original recruitment target of 380 participants. The trial closed to recruitment on 31st March 2019, the last patient recruited was randomised on 1st April 2019 at which point there were 87 randomised participants. All participants were followed up to their 4 months visit; 14 month visit data could only be collected for participants who started laser therapy prior to 6th July 2018. The last patient visit was the 27th October 2019.

3. STATISTICAL CONSIDERATIONS

3.1 Timing of analyses

Participant follow-up visits

Following the decision that the trial would close, the HTA agreed that follow-up could end once the last participant to enter the trial had reached their 4 month follow-up visit. Fourteen month visit data was only collected for participants who started laser therapy prior to 6th July 2018

3.2 Analysis populations

The serious breach

A randomisation schedule was prepared which generated unique coordinates for allocations in a 2-dimensional grid (a 2 digit number of the form (x,y)) – the allocation in the grid at (x,y) corresponded to a treatment allocation (laser or sham). THOR had two grids which had different laser/sham settings:

- grid 1 “Internal SW2 - SW6 in 1 & 2 positions”
- grid 2 “Internal SW2 - SW6 in A & B”.

THOR communicated that the laser machines had been programmed to match grid 1.

As a result of routine laser system testing it became apparent that the randomisation schedule did not match grid 1 (i.e. the allocation recorded in the randomisation log did not always match the laser therapy received). After unblinded testing it was found that the laser machines at all sites had been programmed to match grid 2 and *not* grid 1. At this point 20 participants had commenced laser therapy (involving 5 sites in total). Seven of these 20 participants had received treatment that was opposite to what they would have received in line with grid 1. The seven participants affected continued with the treatment they had started receiving [11]. The randomisation schedule was updated so that subsequent treatment allocations would match grid 2, in line with the machines’ settings. The allocations for the first 20 participants were left unchanged in the randomisation log. The treatment received by the 7 affected participants was documented and stored securely by the NCTU Quality Assurance manager and an extra column was added, by the data manager, to the downloaded randomisation log with the treatment received.

Although the wrong allocation was assigned to seven participants the unique coordinates were generated randomly from the randomisation schedule, hence the allocation procedure was still random and unbiased.

The analyses will follow the intention-to-treat (ITT) principle with the ITT analysis set being modified to allow those participants who received the incorrect treatment at randomisation to be included in the treatment group corresponding to the treatment they received [11].

Modified Intention-to-treat (mITT) analysis set: This population contains all patients randomised into the study (regardless of their adherence with the entry criteria, regardless of subsequent withdrawal from treatment or deviation from the protocol). However, it is a modified ITT analysis set because it will include participants in the treatment group corresponding to the treatment they randomly received (where the randomised (x,y) coordinates for seven participants were used to generate an allocation from the wrong grid).

Statistical analyses will be conducted on complete cases from the mITT analysis set. Participants will be included in analyses if they attended the visit of interest and have evaluable data for the outcome measure of interest. Evaluable data here is non-missing for all outcome measures listed in Section 2.4 except the three questionnaires MDADI, QLQ-C30 and H&N 35, where simple imputation for missing questionnaire items in accordance with the questionnaire’s scoring manual will be used.

Safety population: For the analysis of safety data all randomised patients who received at least one session of laser therapy will be included.

4. STUDY POPULATION

4.1 Participant flow through trial

Patient flow through the trial will be presented using a CONSORT diagram. Information will be provided on numbers and reasons (where appropriate) for: screened patients not being eligible; eligible patients not being randomised; patients found to be ineligible after randomisation; patients deviating from allocated treatment; patients not evaluable for the primary endpoints and withdrawal from follow-up.

Figure 1: CONSORT flow diagram

4.1.1 Screening, eligibility and recruitment

Screening and recruitment will be summarised. Reasons for ineligibility and reasons for eligible patients not being recruited will also be summarised (where available).

The following table and graphs will be included:

Table 2: Number of patients recruited by site per month

Figure 2: Total number of patients recruited by site

Figure 3: Cumulative target and observed recruitment per month

4.1.2 Withdrawals and follow-up

4.1.2.1 Withdrawals

Withdrawals from the trial will be presented in a line listing, noting when the participant withdrew, if routine data was still collected and the reason for withdrawal.

Example Table 3: Line listing of withdrawals from laser therapy

Trial ID	Treatment group	Days from randomisation to withdrawal	Reason for withdrawal	Completion status

Example Table 4: Line listing of complete withdrawals from study

Trial ID	Treatment group	Days from randomisation to withdrawal	Reason for withdrawal	Completion status

4.1.2.2 Participant follow-up

Participants were scheduled to return for their study assessments at the following time points:

Baseline (after consent but before day 1 of laser therapy)

Weeks 1 to 5

Week 6

4 months after end of week 6 laser therapy (± 2 weeks)

14 months after end of week 6 laser therapy (± 2 weeks)

Example Table 5: Participant follow-up by visit and treatment group

		Sham	Laser	Total
Randomisation		n (100%)	n (100%)	n (100%)
Baseline		n (% of randomised)	n (% of randomised)	n (% of randomised)
Week 6		n (% of randomised)	n (% of randomised)	n (% of randomised)
4 months	Compliance with visit window	n (% of randomised)	n (% of randomised)	n (% of randomised)
14 months	Compliance with visit window	n (% of randomised)	n (% of randomised)	n (% of randomised)

4.1.3 Adherence to protocol – laser therapy

Patients are scheduled to receive three laser sessions per week, during weeks one to six of their radiotherapy. Patients will receive LLLT plus standard care or sham LLLT plus standard care 3 times weekly by

a non-contact method for a period of 6 weeks (from day 1 of (C)RT dose). LLLT will be administered ideally within 2 hours, but always before (C)RT session, with a minimum of 24 hours between each of the 3 laser therapy sessions. Each session will last approximately 20-30 minutes, with LLLT at 6 pre-determined anatomical sites in the oral cavity.

LLLТ will be delivered to the patient by nurses, allied healthcare professionals or delegated staff at a convenient time before the (C)RT treatment session (within an hour of the CRT dose). All patients will also receive the standard care offered for OM by each centre. Standard care varies across NHS Trusts but typically consists of oral hygiene instruction, topical analgesics and coating gels.

It is possible that a (C)RT session may be missed due to reasons such as an infection or the patient being unable to attend that visit. The LLLT will be delivered at the next session that the patient is able to attend for their (C)RT treatment as long as a minimum of 24 hours has passed, however data will still be collected wherever possible, particularly if the patient is an in-patient in the hospital.

Laser therapy received and (C)RT treatment interruptions will be summarised as indicated in the following tables.

Example Table 6A: (Chemo-)Radiotherapy treatment and interruptions (n=xx)

Radiotherapy alone			
	Laser (n =)	Sham (n =)	Total (n =)
Aim of radiotherapy, n (%)			
Primary radical radiotherapy			
Adjuvant radiotherapy			
High dose palliative radiotherapy			
Missed radiotherapy, n (%)			
Number of missed fractions Median (IQR) ...Range			
Reason for missing radiotherapy	x reasons (n participants)	x reasons (n participants)	x reasons (n participants)
Adverse Event			
Patient Choice			
Clinical Decision			
Technical or staffing issue			
Other			
Chemo-radiotherapy			
	Laser (n =)	Sham (n =)	Total (n =)
Aim of radiotherapy, n (%)			
Primary radical radiotherapy			

Adjuvant radiotherapy			
High dose palliative radiotherapy			
Missed radiotherapy, n (%)			
Number of missed fractions Median (IQR) ...Range			
Reason for missing radiotherapy	x reasons (n participants)	x reasons (n participants)	x reasons (n participants)
Adverse Event			
Patient Choice			
Clinical Decision			
Technical or staffing issue			
Other			
Type of chemotherapy /biological therapy, n (%)			
Cetuximab			
Cisplatin +/- 5 FU			
Carboplatin			
Other			
Amount per dose Median (IQR) ...Range			
Missed chemotherapy doses, n (%) Number of missed doses Median (IQR) ...Range			

Example Table 6B: laser therapy sessions by week

	Sham (n = xx)						Laser (n = xx)						Overall (n =)					
	Week 1	Week 2	Week 3	Week 4	Week 5	Week 6	Week 1	Week 2	Week 3	Week 4	Week 5	Week 6	Week 1	Week 2	Week 3	Week 4	Week 5	Week 6
Number of patients continuing with laser treatment																		
													n =	n =	n =	n =	n =	n =
Number of laser sessions received																		
0													X (%)					
1																		
2																		
3																		
Missing																		

4.2 Baseline characteristics

Demographic, clinical and baseline characteristics and trial stratification factors: type of planned treatment (radiotherapy alone/chemo-radiotherapy) and type of radiotherapy field (unilateral/bilateral) at randomisation will be summarised across treatment groups descriptively. We will report the number and percentage in each group for all categorical variables (e.g. gender) and mean, SD or median, IQR and range, as appropriate, for all continuous variables. No significance testing will be carried out due to the randomised nature of the study.

Example Table 7: Baseline characteristics

	Sham (n=xx)	Laser (n=xx)	Overall (n=xx)
Age (years), mean (SD)			
Height (cm), mean (SD)			
Weight (kg), mean (SD)			
Gender			
Female			
Male			
Type of planned treatment			
Radiotherapy alone			
Chemo-radiotherapy			
Type of radiotherapy field			
Unilateral			
Bilateral			
Site of disease			
Nasopharynx			
Oropharynx-HPV positive			
Oropharynx-HPV negative			
Oropharynx-HPV undetermined			
Larynx			
Oral			
Unknown Primary			
Missing			
TNM Classification			
Primary Tumour			
TX			
T0			
Tis			
T1			
T2			
T3			
T4			
Missing			
Regional Lymph Nodes			
NX			
NO			
N1			
N2			
N3			
Missing			

Distant Metastasis MX MO M1 Missing			
Patient to receive chemotherapy in addition to radiotherapy? No Yes Missing			
How will the chemotherapy be administered? Concurrent Induction Induction and Concurrent NA Missing			
Patient to have IMRT No Yes			
Patient has had surgery to primary tumour No Yes Missing			
Adult Co-morbidity evaluation (ace-27) None Grade 1 - Mild Decompensation Grade 2 - Moderate Decompensation Grade 3 – Severe Decompensation Unknown Missing			
WHO Mucositis Scale 0 (none) I (mild) II (moderate) III (severe) IV (life-threatening) Missing			

Data are n; %, mean (SD) or median (IQR); range, unless otherwise stated

5. ANALYSIS METHODS

5.1 Primary outcome

Definition of the primary outcome:

The primary outcome is the OMWQ-HN score at week 6 following start of LLLT treatment.

Primary outcome measure

The primary outcome measure is the OMWQ-HN score. The OMWQ-HN was collected at baseline, weekly during weeks 1 to 6 of treatment, and at 4 month follow-up.

[figure not shown]
Responses to the OMWQ-HN will be summed to give a total overall score between 0 and 54 (a higher score indicating poorer wellbeing and oral function). The total score will not be computed for participants who had missing data on ≥ 1 item, with the exception of participants who scored '0' (=no soreness) on question 1 (who would not then proceed to the remaining questions and would be given a total score of 0).

Example Table 8: Completeness of primary outcome data by visit and treatment group

	Laser			Sham			Total					
	n	Fully missing	Partial missing	Complete	n	Fully missing	Partial missing	Complete	n	Fully missing	Partial missing	Complete
Baseline												
Week 1												
Week 2												
Week 3												
Week 4												
Week 5												
Week 6												
4 month												

The OMWQ-HN will be explored graphically using individual participant plots over time and at 6 weeks using histograms or dotplots and/or boxplots by treatment group. The OMWQ-HN will be summarised numerically as mean, standard deviation, median, interquartile range, and range at each time point for each of the treatment groups.

Example Figure 4: Individual participant plots of OMWQ-HN by visit [baseline to week 6]

Example Table 9: Summary statistics for OMWQ-HN over time

Laser								
	Baseline (n =)	Week 1 (n =)	Week 2 (n =)	Week 3 (n =)	Week 4 (n =)	Week 5 (n =)	Week 6 (n =)	4 Month (n =)
Min								
Median (IQR)								
Mean (SD)								
Max								
Sham								
	Baseline (n =)	Week 1 (n =)	Week 2 (n =)	Week 3 (n =)	Week 4 (n =)	Week 5 (n =)	Week 6 (n =)	4 Month (n =)
Min								
Median (IQR)								
Mean (SD)								
Max								
Higher scores on the OMWQ-HN indicate poorer wellbeing and oral function.								

5.1.1 Primary analysis of primary outcome

The difference between treatment group means at week 6 will be reported with 95% confidence interval.

Example Table 10: Mean difference in OMWQ-HN at 6 weeks between treatment groups

[figure not shown]
OMWQ-HN at week 6 Mean(sd)		Difference in means (95% CI) (Sham minus Laser)
Sham (n=)	Laser (n=)	
		Mean diff (95% CI)

(a higher score indicates poorer wellbeing and oral function)

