16.1 Statistical Analysis Plan

The primary analysis of the primary outcome is a comparison of the OMWQ-HN score at 6 weeks following start of RT (+/- 2 weeks) in the two randomised arms. Mean baseline and 6-week scores will be presented (with 95% CI) as well as the mean difference from baseline score. Transformation may be appropriate for non-normally distributed data. The null hypothesis to be tested is H0: mean 6-week score in patients randomised to LLLT = mean 6-week score in patients randomised to sham LLLT. Randomisation is stratified by known clinical confounders of cancer treatment: 1. planned treatment (radiotherapy alone or chemo-radiotherapy 2. Unilateral or bilateral radiotherapy fields.

The size and significance of any treatment effect will be estimated in a multivariable linear regression model adjusting treatment by the stratification factor. Secondary analyses of the primary outcome will adjust the size and significance of any treatment effect by other important baseline clinical covariates (importance assessed through univariate modelling) using multivariable regression and ANCOVA. Underlying assumptions of the regression models and non-linear continuous covariates will be investigated, reported and addressed. A two-sided 5% level of significance will be used.

A sensitivity analysis may be carried out on an imputed dataset, based on multiple imputation methods, to deal with missing data and will be described in the Statistical Analysis Plan, which will be

finalised prior to any analysis of unblinded data.

Comparison of secondary outcome measures has not been powered. As such, descriptive statistics such as means (sd, 95% CI), medians (inter-quartile ranges, range) will be presented by randomised treatment arm for continuous secondary outcome measures, specifically scores, feeding tube days, inpatient admission days, water swallow times. ITT proportions (95% CI) will be calculated and presented for categorical measures.

Time to event summary statistics will be estimated using the method of Kaplan and Meier, and 3, 6 and 12-month estimates (with 95% CI) reported. Differences between 'survival' distributions will be estimated using the hazard ratio (95%CI), unadjusted and adjusted by stratification factors.

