2.3 Randomisation and blinding

Patients are randomised to receive standard care plus LLLT or standard care plus sham LLLT on a 1:1 basis using a method of random permuted blocks of concealed variable block size and stratified by 1: planned treatment (radiotherapy alone or chemo-radiotherapy) 2: Unilateral or bilateral radiotherapy fields. To ensure concealment of allocation, patients are centrally randomised by the Newcastle Clinical Trials Unit using a secure web-based system. It provides ease of operation with in-built validation/plausibility checks at time of data entry. The PI at site or an individual with delegate authority accesses the web based randomisation system and enter in the required information. The system returns a unique patient trial number and the randomised treatment allocation which corresponds to one of the two settings on the laser machine. A telephone and/or email randomisation service will be used should the web based system be unavailable for any reason.

The equipment manufacturer has modified the laser device to deliver the sham treatment. The protective glasses block the red colour of the light and prevent staff delivering the LLLT from knowing if the machine is delivering the sham output or active laser. Staff will operate the machine following the Standard Operating Procedure for the trial and laser safety rules, and the machine will be switched off prior to removal of all safety glasses.

LLLT will be delivered in a locked room with all reflective surfaces covered or absent. The machine will emit audible beeps when delivering both the sham and the intervention. All staff trained to deliver LLLT will wear protective eye glasses as per the laser instructions for use (which comply with EU legal requirements).

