5.1.2 Secondary analysis of primary outcome

The difference between treatment group means at week 6 will be estimated using analysis of covariance (ANCOVA), adjusting for baseline OMWQ-HN. This will be on a complete case basis for those participants with a score at both baseline and 6 week visit. If the assumptions of the ANCOVA model are satisfied an adjusted mean difference between treatment groups at week 6 with 95% CI will be reported. This analysis is equivalent to analysing the change from baseline adjusted for baseline. The baseline and week 6 OMWQ-HN data will be presented graphically:

Example Figure 5: Spaghetti plot, OMWQ-HN score: change from baseline to week 6

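### The SAP's primary analysis leaves out the stratification factors that the supplied protocol adjusts for, so its confidence interval is conservative if those factors are prognostic

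*SAP*

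**What the plan says.** SAP 2.3 states that allocation is "stratified by 1: planned treatment (radiotherapy alone or chemo-radiotherapy) 2: Unilateral or bilateral radiotherapy fields". Protocol 16.1 gives the reason for choosing these two factors: "Randomisation is stratified by known clinical confounders of cancer treatment". The same section then sets the model: "The size and significance of any treatment effect will be estimated in a multivariable linear regression model adjusting treatment by the stratification factor". It writes factor in the singular, but it has just listed two, and I read it as both. Other baseline covariates come second: "Secondary analyses of the primary outcome will adjust the size and significance of any treatment effect by other important baseline clinical covariates".

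The SAP differs. Section 5.1.1 says only "The difference between treatment group means at week 6 will be reported with 95% confidence interval", and Example Table 10 has columns for the two means and their difference, with none for an adjusted estimate. Section 5.1.2 adds a secondary analysis, "estimated using analysis of covariance (ANCOVA), adjusting for baseline OMWQ-HN", without the stratification factors and on a condition: "If the assumptions of the ANCOVA model are satisfied an adjusted mean difference between treatment groups at week 6". In the rest of the SAP the two factors are only described: in the baseline table (4.2) and in the week-6 subgroup summaries (5.3). Section 5.2 adjusts the MDADI and EORTC outcomes for their baseline values, but not for the strata.

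SAP 2.6 reports that recruitment closed with 87 randomised of a planned 380. SAP 1.2.2 and 2.5 refer to protocol version 4.0; the supplied protocol is version 2.1.

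**The concern.** Stratified randomisation balances the arms on the chosen factors, which makes the true sampling variance of the treatment difference smaller. An analysis that ignores the factors leaves their variance in the residual and computes the standard error as if that balance had not been arranged. When the factors predict outcome, the interval is too wide for its nominal level.

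Two things are at stake. One is precision, in a trial that closed at under a quarter of its target (87/380 = 23%). The other is traceability: the adjusted estimate that the supplied protocol makes its main result would appear nowhere in the report, and the SAP does not say why. Early closure could explain giving up formal testing. It does not explain dropping two binary covariates that are known for every randomised patient.

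A smaller issue is that the only adjusted estimate of the primary outcome is reported if model assumptions are judged satisfied. No criterion is given, nor any alternative interval if they are not.

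**Working it through.** **1. The plan's own figure.** Inputs from Protocol 16.4: difference 4 points, SD 10.7, two-sided 5%, power 90%. The normal approximation gives 151 per arm. The noncentral t gives 152 per arm (power 90.1%), and 152/0.80 = 190. The stated 152 and 190 reproduce, so 4 points and SD 10.7 are used below.

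**2. Unadjusted interval at the achieved size.** With the protocol's maximum 20% loss, 87 × 0.80 = 69.6, taken as 70 (35 per arm, an assumption).

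- SE = 10.7 × √(4/70) = 2.56.
- Half-width = t(0.975; 68) × 2.56 = 1.995 × 2.56 = 5.10 points.
- Power for 4 points = 34%.

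If all 87 were evaluable (43 v 44), the half-width would be 4.56 and power 41%. Either interval extends more than 4 points on each side.

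**3. Adding the two stratification factors.** The documents do not say how much week-6 variance the factors explain, so R² is varied. Because the factors are balanced by design, the cost is essentially two degrees of freedom. The residual SD is 10.7 × √(1 − R²). The coverage of the unadjusted interval is approximately 2Φ(1.96/√(1 − R²)) − 1.

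| Strata R² | Residual SD | Adjusted half-width, t(66) | Power for 4 points | Coverage of unadjusted 95% CI |
|---|---|---|---|---|
| 0 | 10.70 | 5.11 | 34% | 95.0% |
| 0.10 | 10.15 | 4.84 | 37% | 96.1% |
| 0.20 | 9.57 | 4.57 | 41% | 97.2% |

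**4. Check by simulation.** 4,000 trials per setting, 70 patients, four strata. Permuted blocks of 4 and factor prevalences of 70% and 75% are assumptions. Mean full widths, unadjusted against strata-adjusted:

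- R² 0: 10.16 v 10.18.
- R² 0.10: 10.19 v 9.68, unadjusted coverage 95.9%.
- R² 0.20: 10.20 v 9.14, unadjusted coverage 97.4%.

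Halving the widths gives 5.08 v 5.09, 5.10 v 4.84 and 5.10 v 4.57, in line with the table. If the strata are uninformative, the loss is about 0.01 of a point.

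**5. Baseline OMWQ-HN.** This score was not stratified on, so chance imbalance carries a penalty. For one covariate the half-width changes by about √(1 − ρ²) × √(1 + 1/(N − 4)). At N = 87 and ρ = 0.2 this is 0.980 × 1.006 = 0.986, a gain of 1.4%. At ρ = 0 there is a loss of 0.6%, at ρ = 0.3 a gain of 4.0%, and at ρ = 0.5 a gain of 12.9%. The documents do not give ρ. Baseline is taken before laser therapy starts, so a low correlation with week 6 is plausible.

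**The case against.** The unadjusted contrast is a legitimate analysis. It is unbiased under randomisation and its interval errs on the wide side, so there is no added risk of a false positive. The main reason for the wide interval is 87 patients instead of 380. The precision gain depends on an R² that the documents do not state. The SAP was written against protocol 4.0, which may have changed section 16.1. All of this stands. It limits the size of the point without removing it: adjusting costs almost nothing even if the factors explain nothing, and the supplied protocol says they matter.

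A reader might infer four stronger things that the documents do not support.

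- **That dropping baseline OMWQ-HN also departs from the protocol.** Protocol 16.1 does not name it in the primary model and leaves other covariates to secondary analyses. SAP 5.1.2 follows that order.
- **That the allocation error makes the raw difference biased.** SAP 3.2 reports that seven of the first 20 participants received the opposite of the logged treatment, and explains that allocation remained random. Planned balance within blocks is no longer assured for those patients, but this slightly weakens the over-coverage argument and does not create bias.
- **That the primary result hangs on an assumption check.** Table 10 is reported in any case; only the secondary ANCOVA is conditional.
- **That adjustment would restore useful power.** It would not. Even if strata and baseline together explained 49% of the variance, power for 4 points with all 87 patients would be about 66%.

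**Conclusion.** The point holds as one of efficiency and traceability. Against protocol 2.1, the SAP removes the stratification adjustment from the primary analysis, restores it in no other model and gives no reason. Whether this departs from the governing protocol has to be confirmed in version 4.0.

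Its size rests on SD 10.7, 70 evaluable patients and an assumed strata R² of 0 to 0.20. Over that range, adjustment changes the half-width by between nothing and about half a point. The unadjusted interval covers about 95% to 97% instead of 95%, and power moves from 34% to at most 41%. The conclusion about benefit or harm is unlikely to turn on this alone. The change should be made because it is nearly free and brings the analysis into line with the design; the trial is not invalid without it.

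**What to change.** - **SAP 5.1.1:** make the primary analysis a linear regression of week-6 OMWQ-HN on treatment and both stratification factors. Report the adjusted difference with its 95% CI, and keep the raw difference in Table 10 as supportive. If the unadjusted estimate is to remain primary, state why and always report the adjusted one beside it.
- **SAP 5.1.2:** add the two factors to the baseline-adjusted ANCOVA and report it always. If assumptions look doubtful, use a robust or bootstrap interval instead of withholding the estimate.
- **Optional:** put baseline OMWQ-HN in the primary model as well. This helps only if it correlates with the week-6 score, and it needs a stated rule that keeps patients whose baseline score is missing. SAP 5.1 leaves the total uncomputed if any item is missing, unless question 1 is scored 0.
- **Traceability:** check section 16.1 of protocol 4.0 and record the reason for any difference.

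The cost is SAP wording, one regression and two degrees of freedom. The factors are recorded at randomisation, so a strata-only model should lose no patient.
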